| | Time to death: -If 'death'='yes', then time to death is calculated as the difference between their date of death and 4.1. If this is 0 (i.e. the patient died on the day of surgery), this will be set to 0.5 days; this is so the patient can be included in the analysis (as Stata excludes outcomes with an event time of 0) |
| | -if 'death'='no' (i.e. the patient was discharged or the patient is still in hospital at day 60), this is the date of discharge or 90 days (whichever is sooner), or 60 days if they are still in hospital then |
| All-cause mortality within 180 days following surgery | This outcome will be defined by two variables: death (yes/no), and the time to death. |
| | For patients in England and Scotland (using government registry death data): |
| | Death: |
| | -'Yes' if the patient died, and the difference between their date of death and 4.1 is less than or equal to 180 |
| | -'No' if the patient died, but the difference between their date of death and 4.1 is greater than 180 |
| | -'No' if the patient did not die |
| | -Missing if the patient died, but their date of death is not available, or if it is |

| | unknown whether the patient died, if 4.1 is missing, or if the date of death is before 4.1 and this discrepancy cannot be resolved |
|---|--|
| | Time to death: -If 'death'='yes', then time to death is calculated as the difference between their date of death and 4.1. If this is 0 (i.e. the patient died on the day of surgery), this will be set to 0.5 days; this is so the patient can be included in the analysis (as Stata excludes outcomes with an event time of 0) |
| | -if 'death'='no', this is set to 180 days |
| | For patients in Wales: |
| | -'Yes' if 7.7 = "Dead"; and the difference between their date of death (in 7.8) and 4.1 is less than or equal to 180 |
| | -'No' if the patient died, but the difference between their date of death and 4.1 is greater than 180 |
| | -'No' if the patient was discharged or still in hospital at day 60 |
| | -Missing if the patient died, but their date of death is not available, or if it is unknown whether the patient died, if 4.1 is missing, or if the date of death is before 4.1 and this discrepancy cannot be resolved |
| | Time to death: -If 'death'='yes', then time to death is calculated as the difference between their date of death and 4.1. If this is 0 (i.e. the patient died on the day of surgery), this will be set to 0.5 days; this is so the patient can be included in the analysis (as Stata excludes outcomes with an event time of 0) |
| | -if 'death'='no' (i.e. the patient was discharged or the patient is still in hospital at day 60), this is the date of discharge or 180 days (whichever is sooner), or 60 days if they are still in hospital then |
| Duration of hospital stay (defined as the number of days from surgery until hospital discharge) | This outcome will be defined by two variables: the discharge event (discharged/died before discharge/censored), and time to the discharge event. |

| | -Discharge event = 'Discharged' if 7.7 = "Alive"; time to discharge event is calculated as difference as the difference in dates between 7.8 and 4.1 |
|---|---|
| | Discharge event - (Died before discharge) if 7.7 - "Dead": time to discharge |
| | is calculated as difference as the difference between the date of death and 4.1 |
| | -Discharge event = 'Censored' if 7.7 = "Still in hospital at 60 days"; time to discharge is 60 days |
| | -Missing if $7.7 =$ "Alive" and 7.8 is missing or 4.1 is missing, or if $7.7 =$ "Dead" and a date of death is not available or 4.1 is missing |
| Hospital re-admission within 180 days of surgery | This outcome will be defined by two variables: the re-admission event (re- admitted/died before re-admission/not re-admitted), and time to the re- admission event. |
| | - Re-admission event = 'Yes' if the patient was re-admitted to hospital within 180 days; time to re-admission event is calculated as the difference between the date of their first re-admission and 4.1 |
| | - Re-admission event = 'Died before re-admission' if the patient died within 180 days and was not re-admitted to hospital; time to re-admission event is calculated as difference as the difference between the date of death and 4.1 |
| | - Re-admission event = 'Censored' if the patient was alive up to 180 days and not re-admitted to hospital; time to re-admission event is 180 |
| | -Missing if the patient was re-admitted but their date of re-admission is not available or 4.1 is missing, or if it is unknown whether the patient was re-admitted, or if 7.7 = "Dead" and a date of death is not available or if 4.1 is missing |

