If there are convergence issues with this analysis approach, we will use the strategy shown in table 2 to find an analysis approach which converges.

Table 1 – Example dataset

| Geographical | Hospital | Time period | Hospital*time | Treatment | Patient |
|--------------|----------|-------------|--------------------|-----------|---------|
| area | | | period interaction | | |
| 1 | 1 | 1 | 1 | 0 | 1 |
| 1 | 1 | 1 | 1 | 0 | 2 |
| 1 | 1 | 2 | 2 | 0 | 3 |
| 1 | 1 | 2 | 2 | 0 | 4 |
| 1 | 2 | 1 | 3 | 0 | 5 |
| 1 | 2 | 1 | 3 | 0 | 6 |
| 1 | 2 | 2 | 4 | 0 | 7 |
| 1 | 2 | 2 | 4 | 0 | 8 |
| 2 | 3 | 1 | 5 | 0 | 9 |
| 2 | 3 | 1 | 5 | 0 | 10 |
| 2 | 3 | 2 | 6 | 1 | 11 |
| 2 | 3 | 2 | 6 | 1 | 12 |
| 2 | 4 | 1 | 7 | 0 | 13 |
| 2 | 4 | 1 | 7 | 0 | 14 |
| 2 | 4 | 2 | 8 | 1 | 15 |
| 2 | 4 | 2 | 8 | 1 | 16 |

Table 2 – Analysis approaches to be used if the primary method of analysis fails to reach convergence

| | Change from previous strategy | Example Stata code |
|---|--|---|
| 1 | Remove the random-effect for the hospital/time-period interaction | mestreg outcome treatment i.time_period age gender i.indication_surgery geo_area: hospital: , distribution(weibull) |
| 2 | Remove the random-effect for hospital | mestreg outcome treatment i.time_period age gender i.indication_surgery geo_area: , distribution(weibull) |
| 3 | Adjust for the fixed-effect of time as a continuous covariate using restricted cubic splines with 7 knot points (where rcs_time_period* are the variables forming the restricted cubic spline) | mestreg outcome treatment rcs_time_period* age gender i.indication_surgery geo_area: , distribution(weibull) |

Secondary outcomes

All-cause mortality up to 180 days

All-cause mortality up to 180 days following surgery and hospital re-admission within 180 days of surgery will be analysed using the same approach as the primary outcome.

Duration of hospital stay

Duration of hospital stay will be analysed using a competing-risk time-to-event model, which recognises mortality as a competing risk for hospital discharge. Because there are no facilities for analysing competing risk data using mixed-effects models in Stata, we will use robust standard errors which account for clustering by geographical area. This analysis will be implemented in Stata as follows:

stset cc_time_to_discharge, failure(cc_discharge == 1)

stcrreg treatment i.time_period age gender i.indication_surgery, compete(cc_discharge == 2) vce(cluster geo_area)

Where:

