cc_discharge is a variable indicating whether the patient was discharged home (=1), died in hospital (=2), or was censored (=0), and *cc_time_to_discharge* is a variable indicating the time to the event.

Hospital re-admission within 180 days

This outcome will be analysed using a competing-risk time-to-event model, which recognizes mortality as a competing risk for hospital re-admission. It will be implemented using the same code as *duration of hospital stay* above.

Secondary analyses of the primary outcome

Evaluating the effect of the intervention over time

We will perform a secondary analysis of the primary outcome to evaluate the effect of the intervention over time (i.e. whether the intervention effect improves over time). This analysis will include patients who presented to hospital during the 5-week period immediately after implementation of the quality improvement intervention. We will evaluate the following four groups:

- Usual care;
- The quality improvement (QI) intervention implemented for less than 5 weeks
- The QI intervention was implemented for 5 weeks or more and less than 10 weeks
- The QI intervention was implemented for 10 weeks or more

This analysis will allow us to determine whether the effectiveness of the QI intervention improves over time. The analysis will be implemented using the same method as for the primary analysis of the primary outcome.

Inclusion of other patient populations which may be affected by the intervention

We will perform a sensitivity analysis to assess whether results are generalisable to other patient populations which may have been affected by the intervention. This includes patients who underwent laparoscopic surgery, and patients who are aged 18-40 years.

Due to the small number of patients in these groups, we will summarise results descriptively, rather than undertaking a formal statistical analysis. We will summarise the number (%) of patients in the treatment arms who experience a primary outcome event. The denominator for this analysis will include patients who either underwent laparoscopic surgery or were aged 18-40 years (or both), and who met all other eligibility criteria.

Process measures

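### The 0.5-day rule for event times of 0 is missing from the length-of-stay and re-admission derivations, and a leftover clause assigns re-admission to the wrong model

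*SAP*

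**What the plan says.** **Zero event times.** Appendix 3 gives the mortality rule four times: for 90-day and 180-day mortality, each for England and Scotland and again for Wales. The rule is "If this is 0 (i.e. the patient died on the day of surgery), this will be set to 0.5 days", and the reason given is that "Stata excludes outcomes with an event time of 0".

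The next two rows of the same table have no such rule. For duration of stay and for re-admission, the time for a patient who dies first "is calculated as difference as the difference between the date of death and 4.1". For a patient discharged alive it is "calculated as difference as the difference in dates between 7.8 and 4.1". In the re-admission row the competing event applies "if the patient died within 180 days and was not re-admitted to hospital". Section 5 analyses duration of stay with `stset` followed by `stcrreg`, and re-admission re-uses that code.

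**Model for re-admission.** Section 5, under the 180-day mortality heading, says that "hospital re-admission within 180 days of surgery will be analysed using the same approach as the primary outcome". That approach is a mixed-effects Weibull model. A little later, under re-admission's own heading, Section 5 says: "This outcome will be analysed using a competing-risk time-to-event model, which recognizes mortality as a competing risk for hospital re-admission".

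**The concern.** The authors know that their software discards a record with time 0 and supply a remedy, but only for two of the four time-to-event outcomes. In the other two, a death on the day of surgery also has time 0. These patients are competing events, which the chosen model exists to retain. Losing them selects the analysis set on outcome and departs from the intention-to-treat population in Section 5.

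The second point is a contradiction in the current text. The two models for re-admission differ in two ways:

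- **Estimand.** A Weibull model for time to re-admission would treat death as censoring. The competing-risk model keeps it as a separate event.
- **Clustering.** The first uses three random intercepts. The second uses robust standard errors clustered by geographical area.

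Two of the three secondary outcomes are touched.

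**Working it through.** **1. Does anything else in the SAP cover a time of 0?**

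- Section 5 includes all eligible patients with available outcome data.
- The inclusion algorithm in Appendix 2 has no exclusion for death on the day of surgery.
- The definitions of a missing outcome in the duration-of-stay and re-admission rows do not mention a time of 0. A patient with a known date of death and a known field 4.1 is therefore not missing.
- No general rule elsewhere extends the 0.5-day reset.
- Field 4.1 records date and time, so differences might be thought fractional. But Appendix 3 measures outcomes from the date of surgery, and the mortality rows treat a death on that day as a difference of exactly 0.
- Very early deaths are foreseen: process measure 10 in Appendix 4 has a category for death before leaving the theatre complex.

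By the SAP's own account of Stata, these patients are dropped from both analyses.

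**2. How many patients?**

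The plan's own total reproduces: 90 hospitals × 17 periods × 18 patients = 27,540. Removing one five-week period per hospital leaves 27,540 − 90 × 18 = 27,540 − 1,620 = 25,920.

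Let d be the share who die on the day of surgery. The SAP does not give it, so 0.25% to 3% is an assumption. If F is the true cumulative incidence of discharge, the incidence among retained patients is F/(1 − d). F = 0.80 is also assumed.

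| d | Dropped (25,920 × d) | Factor 1/(1 − d) | 0.80 becomes |
|---|---|---|---|
| 0.25% | 65 | 1.003 | 0.802 |
| 1% | 259 | 1.010 | 0.808 |
| 2% | 518 | 1.020 | 0.816 |
| 3% | 778 | 1.031 | 0.825 |

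**3. What happens to the treatment effect?**

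Take the same true incidence F in both arms and write d_C and d_I for the day-0 shares under usual care and intervention. The apparent subdistribution hazard ratio at the end of follow-up is

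sHR = ln[1 − F/(1 − d_I)] / ln[1 − F/(1 − d_C)].

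With d_I = d_C it is 1.00. The other rows assume that the intervention halves d. F = 0.20 for re-admission is likewise assumed.

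| d_C to d_I | Discharge, F = 0.80 | Re-admission, F = 0.20 |
|---|---|---|
| 1% to 1% | 1.000 | 1.000 |
| 1% to 0.5% | 0.987 | 0.994 |
| 2% to 1% | 0.974 | 0.989 |
| 3% to 1.5% | 0.960 | 0.983 |

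For example, with F = 0.80 and 3% to 1.5%: 0.80/0.985 = 0.8122 and 0.80/0.97 = 0.8247, so sHR = ln(0.1878)/ln(0.1753) = 1.672/1.741 = 0.960.

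**4. Which re-admission model is meant?**

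| Place in the SAP | Model |
|---|---|
| Section 1, changes from protocol | Competing-risk |
| Section 5, re-admission's own heading | Competing-risk, with the duration-of-stay code |
| Appendix 3, re-admission row | Re-admitted, died before re-admission or not re-admitted, which fits only a competing-risk model |
| Section 5, 180-day mortality heading | As the primary outcome (mixed-effects Weibull) |

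Three places agree, and the fourth is a clause under another outcome's heading.

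**The case against.** The strongest reply is that these are two drafting slips with little consequence. The authors plainly know the remedy for zero times and left it out of two table rows; they did not decide to analyse a different population. The death rate used above is assumed, and the inflation factor describes incidence within an arm, whereas the planned inference is on a treatment effect, which does not move when the rate is equal in both arms. Nothing in the SAP suggests that the intervention would halve deaths on the day of surgery. All of this stands, and it limits the size of the point. It does not remove it, because the derivation as written still drops patients whom the stated population includes.

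Two stronger readings are tempting, and the SAP supports neither.

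- **That the patients would vanish unnoticed.** Section 5 promises a summary of the number excluded from each analysis with reasons, and dummy Table 2 in Appendix 1 has missing-data columns by arm. The loss should be visible, though reporting it does not put it right.
- **That the re-admission model could be picked after seeing results.** Section 1 does record that the changes from version 2.0 followed the trial statistician's access to data. But it also lists the competing-risk model as a change from protocol, and the model's own heading and the derivation agree. An analyst who used the Weibull model would contradict all three. The clause is best read as leftover text.

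**Conclusion.** Both points hold as errors of wording, with modest consequences.

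As written, deaths on the day of surgery, and any same-day discharge or re-admission, drop out of the duration-of-stay and re-admission analyses. On an assumed day-0 death rate of 0.25% to 3%, that is 65 to 778 of about 25,920 patients, with cumulative incidence of discharge overstated by a factor of about 1.003 to 1.03. The subdistribution hazard ratio is essentially unchanged if the rate is equal in both arms. If a rate of 1% to 3% were halved by the intervention, it would move from 1.00 to between 0.987 and 0.960 for discharge, and to between 0.994 and 0.983 for re-admission. These figures rest on the assumed rates, on assumed incidences of 0.80 and 0.20, and on equal true incidence in both arms. A reader might infer that the treatment effects are biased in any event; that needs a difference in day-0 deaths between arms, for which the SAP gives no evidence.

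The re-admission clause contradicts the rest of the SAP, but the intended model is clear. No numerical size is put on this part, because the SAP gives no re-admission rate.

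The primary outcome, 180-day mortality and the power calculation are unaffected. The corrections are worth making because the plan should not discard patients it says it will analyse.

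**What to change.** 1. In Appendix 3, add to the duration-of-stay and re-admission rows that any event time of 0 is set to 0.5 days, whatever the event type. One general sentence above the table, covering all four outcomes, would do the same.
2. In Section 5, under the 180-day mortality heading, delete the words that add re-admission to that sentence, so that only the competing-risk model under re-admission's own heading remains.

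The cost is two wording edits. No new data are needed, and both edits follow conventions and intentions that the SAP already states.

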Appendix 4: Calculating process measures

- 1. Consultant led decision to operate
- 2. When consultant led decision to operate, did this consultant personally review patient at time of decision?
- 3. Preoperative documentation of risk
- 4. Time from decision made to operate to entry into operating theatre
- 5. Patient entered operating theatre within time-frame specified based on their urgency level (i.e. <2 hours, 2-6 hours, 6-18 hours, or >18 hours)
- 6. Consultant surgeon present in operating theatre
- 7. Consultant anaesthetist present in operating theatre
- 8. Goal directed fluid therapy used during surgery
- 9. Arterial lactate measured at end of surgery
- 10. Critical care admission immediately after surgery

| Process measure | Calculation |
|---|--|
| 1. Consultant led decision to operate | -'Yes' if 2.4 = "Consultant" |
| | |
| | -'No' if 2.4 is anything other than "Consultant" |
| | -Missing if 2.4 is missing |
| 2. When consultant led decision to operate, did this | -'Yes' if 2.5 = "Yes" |
| consultant personally review patient at time of decision? | |
| | -'No' if 2.5 = "No" |
| | Missing if 2 F |
| | -IVIISSING IF 2.5 = "UNKNOWN" |
| | *Note: patients for whom 2.4 is not "Consultant" are |
| | excluded. |
| 3. Preoperative documentation of risk | -'Yes' if 3.1 = "low (<5%)" or "medium (5-10%)" or |
| | "high (>10%)" |
| | |
| | -'No' if 3.1 = "Not documented" |
| | -Missing if 3.1 is missing |
| 4. Time from decision made to operate to entry into | -calculated as the difference between date/time in 4.1 |
| operating theatre | and the date/time in 2.2 |
| | |

| | -missing if either 2.2 or 4.1 are missing/not known |
|--|--|
| 5. Patient entered operating theatre within time-frame | -'Yes' if (4) is less than or equal to time specified in |
| specified based on their urgency level (i.e. <2 hours, 2-6 | 3.22 |
| hours, 6-18 hours, or >18 hours) | |
| | -'No' if (4) is more than time specified in 3.22 |
| | |
| | Missing if (4) or 3.22 is missing |
| 6. Consultant surgeon present in operating theatre | -'Yes' if 4.2 = "Consultant" |
| | |
| | -'No' if 4.2 is anything other than "Consultant" |
| | |
| | -Missing if 4.2 is missing |
| 7. Consultant anaesthetist present in operating theatre | -'Yes' if 4.3 = "Consultant" |
| | |
| | -'No' if 4.3 is anything other than "Consultant" |
| | |
| | -Missing if 4.3 is missing |
| 8. Goal directed fluid therapy used during surgery | -'Yes' if 4.4 = "Cardiac output monitor" or "Other" |
| | |
| | -'No' if 4.4 = "Not provided" |
| | |
| | -Missing if 4.4 is missing |
| 9. Arterial lactate measured at end of surgery | -'Yes' if 6.3 = any number |
| | |
| | -'No' if 6.3 = "Not performed" |
| | |
| | -Missing if 6.3 is missing |
| 10. Critical care admission immediately after surgery | -'Yes' if 6.24 = "Level 2 HDU" or "Level 3 ICU" |
| | |
| | - 'No' if 6.24 = "Ward" |
| | |
| | -Missing if 6.24 is missing |
| | |
| | *Note: patients for whom 6.24 = "Died prior to |
| | discharge from theatre complex" will be excluded |
| | from the denominator |

Appendix 5: Calculating indication for surgery

The variable 'indication for surgery' (which will be included in the regression models for the clinical outcomes) will be derived as in the following table:

| Indication for surgery category | Calculation |
|---------------------------------|---|
| Peritonitis | -if 5.2 = "Peritonitis" |
| Perforation | -if 5.2 = "Perforation" |
| Abdominal infection | -if 5.2 = "Abdominal abscess" or "Sepsis" |
| | or "Intestinal fistula" |
| | or "Phlegmon" |
| Intestinal obstruction | -if 5.2 = "Intestinal obstruction" |
| | or "Small bowel obstruction" |
| | or "Large bowel obstruction" |
| | or "Volvulus" |
| | or "Intussusception" |
| | or "Obstructing incisional hernia" |
| Haemorrhage | -if 5.2 = "Haemorrhage" |
| Ischaemia | -if 5.2 = "Ischaemia" or "Necrosis" |
| Other | -if 5.2 = "Colitis" |
| | or "Abdominal wound dehiscence" |
| | or "Abdominal compartment syndrome" |
| | or "Anastomotic leak" |
| | or "Other (Please give details)" or "Incarcerated |
| | hernia" |
| | or "Pneumoperitoneum" |
| | or "Pseudo-obstruction" |
| | or "Internal hernia" |
| | or "Acidosis" |
| | or "latrogenic injury" |
| | or "Foreign body" |
| Multiple indications | -if ≥2 of the above categories are 'Yes' |
